3.6 DURATION OF THERAPY

Subjects will continue to receive study treatment until the occurrence of any of the events described in Section 3.12.

Subjects showing clinical benefit and who are tolerating study treatment may remain on study until the end of study, defined as 36 months after the last subject is enrolled. Subjects who are still on treatment at the end of the study and deriving clinical benefit from acalabrutinib monotherapy may be eligible to enroll in a rollover or safety extension study of acalabrutinib monotherapy (see Section 3.0).

3.7 ASSESSMENT OF DOSE-LIMITING TOXICITY

In Part 1, a DLT will be defined as the occurrence of any of the following ACP-319-related AEs:

- 1. Any Grade ≥3 nonhematologic toxicity (except Grade 3 nausea, vomiting, or diarrhea that respond to supportive therapy)
- 2. Any of the following hematologic toxicities (for CLL):
 - a. Grade 4 neutropenia lasting >7 days
 - b. Grade 4 thrombocytopenia, or Grade 3 thrombocytopenia with bleeding, or any requirement for platelets transfusion
 - c. Grade 3 febrile neutropenia (temperature ≥38.5°C)
 - d. Grade 4 anemia, unexplained by underlying disease
- 3. Dosing delay due to toxicity for >28 consecutive days

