1.13.2 ACP-319 First-in-Human Study

ACP-319 monotherapy has been evaluated in a first-in-human trial (FIH), dose-escalation study (25 to 400 mg QD) in subjects with relapsed or refractory lymphoid malignancies (Amgen Study #20101262/NCT01300026). Key eligibility criteria included requirements that subjects be ≥18 years old, have an Eastern Cooperative Oncology Group (ECOG) performance status ≤2, and demonstrate adequate organ function. ACP-319 was administered until disease progression or unacceptable toxicity. DLTs were evaluated during the first 28 days of ACP-319 administration.

Enrollment in this study is complete. Because the protocol allowed subjects to continue with ACP-319 treatment until disease progression or intolerable AE, the study is still ongoing. The results from the most recent clinical database review, 31 October 2013, are provided below.

Twenty-eight subjects received ACP-319 (6 at 25 mg; 3 at 50 mg, 100 mg, 200 mg, and 300 mg; and 10 at 400 mg; all doses were given QD). The most common AEs experienced by subjects during the initial assigned dose levels (in at least 25% of subjects) were cough 13 (46%), diarrhea 13 (46%), fatigue 10 (36%), pyrexia 10 (36%), nausea 9 (32%), and anemia 7 (25%). SAEs that occurred in >1 subject each were febrile neutropenia, disease progression, device-related infection, lung infection, and pneumonia (each 2 subjects [7%]), and pyrexia (3 subjects [11%]). SAEs that were assessed by the investigator to be treatment-related (including those occurring after intrasubject dose escalation) occurred in 6 subjects: hemolysis, hypoxia, and pneumonia; hemolysis; pyrexia, *Clostridium difficile* colitis, and infection; abdominal pain and decreased appetite; colitis, neutropenia, and febrile neutropenia; and exfoliative dermatitis.

One subject experienced a DLT (Grade 3 hemolysis). This subject had received rasburicase on the same day as ACP-319; rasburicase is associated with hemolysis and methemoglobinemia and includes a "black box" warning for these events (ELITEK [prescribing information] 2011). One subject died due to a thromboembolic event that was assessed by the investigator as unrelated to ACP-319, and 1 subject died due to disease progression. A trend towards QTcF prolongation was noted in the 400-mg cohort; however, no QTcF >500 msec or increase >60 msec from baseline has been observed.

[figure not shown]

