3.0 STUDY DESIGN

This study is a multicenter, open-label, nonrandomized, sequential group, dose-escalation study to be conducted at approximately 30 sites. The study is divided into 2 parts: Part 1 of the study is the dose-escalation portion and Part 2 allows for possible expansion groups (Figure 3-1).

Protocol: ACE-LY-001

A cycle is defined as a period of 28 days.

Part 1

In each dose-escalation cohort, subjects will take acalabrutinib (and previously ACP-319) BID at approximately 12-hour intervals. The acalabrutinib dose will be fixed at 100 mg BID. The ACP-319 dose will be escalated as follows:

Cohort 1: Acalabrutinib 100 mg BID + ACP-319 25 mg BID continuously

Cohort 2: Acalabrutinib 100 mg BID + ACP-319 50 mg BID continuously

Cohort 3: Acalabrutinib 100 mg BID + ACP-319 100 mg BID continuously

Each dosing cohort will be enrolled sequentially with 6 subjects per cohort. If ≤1 dose-limiting toxicity (DLT) (see below for definition) is observed in the cohort during Cycle 1, escalation to the next cohort will proceed. If ≥2 DLTs are observed during Cycle 1, dosing at that dose and higher will be suspended and the maximum tolerated dose (MTD) will be established as the previous cohort. The MTD is defined as the highest daily dose for which fewer than 33% of the subjects experience a DLT during Cycle 1. Escalation will end with Cohort 3 or sooner if the MTD is reached in an earlier cohort.

Part 1 of the study will include adult subjects with the following disease types:

Non-germinal center B-cell subtype (non-GCB) diffuse large B-cell lymphoma (DLBCL), characterized as de novo

MCL, characterized by documentation of monoclonal B cells that have a chromosome translocation t(11;14)(q13;q32) and/or overexpress cyclin D1 iNHL

- o FL Grade 1, 2 or 3a
- o WM
- o CLL/SLL

Note: Under Amendment 6 of this protocol, all active subjects will receive acalabrutinib monotherapy (100 mg BID).

Part 2

Part 2 consists of expansion groups of up to 12 subjects per histology provided the safety and efficacy results from Part 1 of the study indicate that further evaluation of the combination is warranted. The possible expansion groups for Part 2 could include adult subjects with the following disease types:

Non-GCB DLBCL, characterized as de novo

Protocol: ACE-LY-001

Germinal center B-cell subtype (GCB) DLBCL

Richter's syndrome

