Subjects showing clinical benefit and who are tolerating study treatment may remain on study until the end of study, defined as 36 months after the last subject is enrolled. Subjects who are still on treatment at the end of the study and deriving clinical benefit from acalabrutinib monotherapy may be eligible to enroll in a rollover or safety extension study of acalabrutinib monotherapy.

[figure not shown]
Subjects who are still on treatment at the end of the study and deriving clinical benefit from acalabrutinib treatment may continue treatment. At the time of the final data cutoff and database closure, subjects who remain in this study may be transitioned to a separate rollover study or remain within this study for continued access to study drug. Once all active subjects are eligible to continue to receive acalabrutinib and after database closure, this study would be considered closed. There will be no further data collection other than reporting of SAEs per Section 6.3. Access within this study will enable continued treatment with visit assessments per standard of care, whereas the separate rollover study will enable treatment continuation with visit assessments and data collection per the rollover study protocol.

Subjects who meet criteria of progressive disease and are continuing to gain clinical benefit from therapy may be able to temporarily remain on acalabrutinib after discussion with the medical monitor.

Protocol: ACE-LY-001

Figure 3-1. Study Schema

Abbreviations: B-ALL = B-cell acute lymphoblastic leukemia; BID = twice daily; CLL/SLL = chronic lymphocytic leukemia/small lymphocytic lymphoma; DLT = dose-limiting toxicity; FL= follicular lymphoma; GCB = germinal center B-cell diffuse large B-cell lymphoma; MM = multiple myeloma; MTD = maximum tolerated dose; non-GCB DLBCL = non-germinal center B-cell diffuse large B-cell lymphoma; RS = Richter's syndrome; TBD = to be determined; WM = Waldenström macroglobulinemia.

Note: Under Amendment 3 of this protocol, subjects with CLL/SLL in Parts 1 and 2 will receive acalabrutinib monotherapy (100 mg BID).

Note: Under Amendment 4 of this protocol, enrollment in Part 2 is closed for all cohorts except the non-GCB DLBCL cohort.

Note: Under Amendment 5 of this protocol, subjects still deriving clinical benefit from monotherapy may be eligible to enroll in a rollover or safety extension study of acalabrutinib monotherapy.

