3.5 STUDY DRUG DOSING

Regimens:

Part 1:

The acalabrutinib dose will be fixed at 100 mg BID. The ACP-319 dose will be escalated as follows:

Cohort 1: Acalabrutinib 100 mg BID + ACP-319 25 mg BID continuously

Cohort 2: Acalabrutinib 100 mg BID + ACP-319 50 mg BID continuously

Cohort 3: Acalabrutinib 100 mg BID + ACP-319 100 mg BID continuously

Twenty-eight days of study drug administration is defined as 1 cycle. Each dosing cohort will be enrolled sequentially with 6 subjects per cohort. If ≤1 DLT (see Section 3.7 for definition) is observed in the cohort during Cycle 1, escalation to the next cohort will proceed. If ≥2 DLTs are observed during Cycle 1, dosing at that dose and higher will be suspended and the MTD will be established as the previous cohort. The MTD is defined as the largest daily dose for which fewer than 33% of the subjects

Protocol: ACE-LY-001

experience a DLT during Cycle 1. Escalation will end with Cohort 3 or sooner if the MTD is reached in an earlier cohort.

Note: Under Amendment 3 of this protocol, subjects with CLL/SLL will receive acalabrutinib monotherapy (100 mg BID).

Part 2:

Acalabrutinib 100 mg BID and ACP-319 50 mg BID continuously.

Note: Under Amendment 3 of this protocol, subjects with CLL/SLL will receive acalabrutinib monotherapy (100 mg BID).

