| Grade ≤2 | Maintain current dose level and schedule. | Maintain current dose level and schedule. | | | |
| Grade 3 | Maintain current dose level and schedule. | Maintain current dose level and schedule. Monitor ANC at least 1x per week. | | | |
| Grade 4 | Maintain current dose level and schedule and monitor ANC at least 1x per week. If Grade 4 neutropenia lasts for >7 days (neutrophil growth factors are permitted per ASCO guidelines [Smith et al. 2015b] and use must be recorded on the CRF), modify dose as instructed in Table 3-1. | Withhold ACP-319. Monitor ANC at least 1x per week until ANC ≥0.5 x 10 ⁹ /L, then resume ACP-319 at lower dose level (if applicable). | | | |
| | Thrombocytopenia | 1 | | | |
| Grade ≤2 | Maintain current dose level and schedule. | Maintain current dose level and schedule. | | | |
| Grade 3 | If no significant bleeding, maintain current dose level and schedule. In the presence of significant bleeding, modify dose as instructed in Table 3-1. | Maintain current dose level and schedule. Monitor PLT at least 1x per week. | | | |
| Grade 4 | Modify dose as instructed in Table 3-1. | Withhold ACP-319. Monitor PLT at least 1x per week until PLT ≥25 x 10 ⁹ /L, then resume ACP-319 at lower dose level (if applicable). | | | |
| | Rash | T | | | |
| Grade 1 | Maintain current dose level and schedule. | Maintain current dose level and schedule. | | | |
| Grade 2 | Maintain current dose level and schedule. | Withhold ACP-319 until Grade ≤1, consider systemic corticosteroids. May resume ACP-319 at initial or lower dose (if applicable) at investigator discretion. | | | |

Protocol: ACE-LY-001

Table 3-2. Recommendations for Acalabrutinib and ACP-319 Dose Modifications Based on Type and Severity of Treatment-Related Adverse Events or Laboratory Abnormalities

| | Recommendation | | |
|-------------------------------------|-----------------------------------|---------------------------------|--|
| NCI CTCAE Grade | Acalabrutinib | ACP-319 | |
| | Withhold acalabrutinib until | Discontinue ACP-319 | |
| | Grade ≤1, consider systemic | permanently. | |
| Grade = 3 or 4 | corticosteroids. May resume | | |
| 014de - 3 01 4 | acalabrutinib at initial or lower | | |
| | dose level (if applicable) at | | |
| | investigator discretion. | | |
| QTC Interval Prolongation | | | |
| | | Refer to Section 4.1.9. | |
| Other Nonhematologic Adverse Events | | | |
| Grade ≤2 | Maintain current dose level | Maintain current dose level and | |

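### Hematologic DLT criteria cover CLL only, so the pooled Part 1 DLT count can miss cytopenias in the other histologies and can only err low

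*Protocol*

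**What the plan says.** Section 3.7 defines a Part 1 DLT as an ACP-319-related adverse event meeting one of three criteria. Criterion 1 is Grade 3 or higher nonhematologic toxicity, with exceptions for some gastrointestinal events. Criterion 2 opens with "Any of the following hematologic toxicities (for CLL" and lists prolonged Grade 4 neutropenia (2a), thrombocytopenia (2b), febrile neutropenia (2c) and Grade 4 anemia (2d). Criterion 3 is a toxicity-related dosing delay of more than 28 consecutive days. The synopsis carries the same CLL qualifier.

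Section 3.0 lists the histologies under "Part 1 of the study will include adult subjects with the following disease types": non-GCB DLBCL, MCL, FL, WM and CLL/SLL. Section 3.5 sets the rule: "If ≤1 DLT (see Section 3.7 for definition) is observed in the cohort during Cycle 1, escalation to the next cohort will proceed". Section 3.0 defines the MTD as the "highest daily dose for which fewer than 33% of the subjects experience a DLT during Cycle 1". Neither the rule nor the MTD definition is split by histology, and no other section gives the non-CLL histologies a hematologic DLT criterion.

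A note to Figure 3-1 adds: "Under Amendment 3 of this protocol, subjects with CLL/SLL in Parts 1 and 2 will receive acalabrutinib monotherapy (100 mg BID".

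**The concern.** The escalation decision and the MTD rest on one pooled count, but the definition behind it differs by disease. A Cycle 1 cytopenia that is a DLT in a CLL subject is not one in an MCL or DLBCL subject on the same dose. Section 5.1 says the rules make a dose increase unlikely when the true DLT rate is high. That assurance covers only the toxicity the definition can count. Characterizing the safety of the combination is the primary objective (Section 2.1), so a DLT or MTD statement that leaves out most histologies' cytopenias could make the combination look better tolerated than it was.

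**Working it through.** **1. The plan's own figures.** Three cohorts of 6 give 3 × 6 = 18, the stated Part 1 maximum. One DLT in 6 is 16.7%, below 33%; two in 6 is 33.3%, not below 33%. The escalation rule and the MTD definition agree with each other. The problem is what enters the count.

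**2. One event taken through the definition.** Suppose an MCL subject on the combination has ACP-319-related Grade 4 neutropenia lasting 10 days in Cycle 1.
- Criterion 1: not met, because the event is hematologic.
- Criterion 2: item 2a describes it, but the list is confined to CLL.
- Criterion 3: a cycle is 28 days (Section 3.5). With dosing on Day 1, the longest hold inside Cycle 1 runs from Day 2 to Day 28, which is 27 days. A delay of more than 28 days cannot be completed in the window.

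Contribution to the count: 0. The same event in a CLL subject on the combination contributes 1. A non-CLL subject is still counted if a Grade 3 or higher ACP-319-related nonhematologic event occurs as well. The counted number is therefore at most the full number, and the error has one direction.

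**3. What it takes to change a decision.** A cohort recorded at 1 of 6 with one uncounted event in another subject would be 2 of 6 (33.3%) and would stop. A cohort recorded at 0 of 6 needs two such subjects. No assumed rate is needed for this.

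**4. Effect on the stated operating characteristic (assumed inputs).** With true DLT rate p, P(escalate) = (1−p)^6 + 6p(1−p)^5. If a share h of DLTs is hematologic, the countable rate in a non-CLL subject is p(1−h). The protocol gives neither p, h nor the mix.

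| p | Full count | As written, no CLL, h = 25% / 50% / 75% | As written, 2 of 6 CLL, h = 25% / 50% / 75% |
|---|---|---|---|
| 33.3% | 0.352 | 0.535 / 0.737 / 0.917 | 0.469 / 0.601 / 0.742 |
| 50% | 0.109 | 0.274 / 0.534 / 0.833 | 0.206 / 0.343 / 0.523 |

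These figures show the mechanism; they do not estimate this trial.

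**5. The only hematologic figure in the document, as a labelled illustration.** Section 1.13.2 reports on 28 subjects given ACP-319 alone: "SAEs that were assessed by the investigator to be treatment-related (including those occurring after intrasubject dose escalation) occurred in 6 subjects". One of them had "colitis, neutropenia, and febrile neutropenia". Taking 1/28 = 3.6% as a hematologic risk, independent of an assumed 20% nonhematologic risk, the combined risk is 1 − 0.80 × 27/28 = 0.229. With no CLL subjects, P(escalate) is 0.655 as written and 0.585 with a full count. At an assumed 10% nonhematologic risk it is 0.886 and 0.818.

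This proxy is weak. It is an any-time serious event, and 13 of the 28 subjects took 300 or 400 mg daily, against 50, 100 or 200 mg daily in Part 1. The same subject had colitis, which criterion 1 would count if it was Grade 3 or higher, so independence is doubtful. That study's own 28-day DLT window recorded one DLT, hemolysis after same-day rasburicase, and no neutropenia, thrombocytopenia or febrile neutropenia; its DLT definition is not shown.

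**The case against.** The strongest reply is that nothing turns on this now. ACP-319 has been stopped. Part 2 was fixed at 50 mg BID, below the top Part 1 dose of 100 mg BID, and the MTD is not a stated objective. Safety teleconferences came before each new cohort (Section 3.14). Adverse events are to be tabulated by severity and drug relationship (Section 5.4.1), with analyses by dosing cohort or cancer type as appropriate (Section 5.1). All of this is correct and lowers the stakes: rewording the definition changes no dosing decision, and cytopenias will be visible somewhere in the safety tables. None of it changes the DLT count, or an MTD or tolerability statement that quotes it.

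The qualifier might be read as a grading note for CLL. Items 2a-2d contain no CLL-specific grading and adverse events are graded by CTCAE, so the plain reading is a restriction. The design rationale is referred to Protocol Amendment 5 (Section 3.2), which is not at hand and may give a reason.

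Three stronger readings are tempting and are not supported.
- **Table 3-2 contradicts Section 3.7.** For Grade 4 neutropenia it says "Withhold ACP-319. Monitor ANC at least 1x per week until ANC" recovers, in any histology. Dose-modification triggers and DLTs serve different purposes: the same table holds ACP-319 for Grade 2 rash, which is no DLT either.
- **Criterion 2 applied to nobody.** Once Amendment 3 moved CLL/SLL subjects to acalabrutinib alone, it reaches no combination subject. The document does not say whether Part 1 was complete by then, and CLL subjects who finished Cycle 1 on the combination earlier were covered.
- **An unsafe dose was carried forward.** The protocol reports no Part 1 events from which this could be judged.

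**Conclusion.** The definition as written leaves ACP-319-related Cycle 1 cytopenias in non-CLL subjects out of the count that drives escalation and the MTD. On this account the Part 1 DLT count can only be biased low. This rests on the plain reading of the CLL qualifier, which appears in both places, and on Cycle 1 as the counting window.

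The size is unknown, and the bias is zero if no qualifying non-CLL event occurred. The gap of about 7 percentage points in the 1/28 illustration should not be quoted as an expected effect, and the larger shifts in the table depend wholly on assumed rates. What can be said without assumptions is that one uncounted event in another subject would reverse escalation from a cohort recorded at 1 of 6. The point is worth correcting because the remedy is small and decides whether the reported tolerability of the combination stands.

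**What to change.** Leave the DLT count as defined. Add one table of ACP-319-related Cycle 1 events meeting 2a-2d, by dose cohort, for all treated Part 1 subjects on the combination, regardless of histology. Include any subject replaced under Section 3.3.3: a non-CLL subject who stopped for such a cytopenia would have had no DLT on the books and so could have been replaced.

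Show this table beside the DLT count and base any MTD or tolerability statement on both. If it shows no extra event, say so; the count as defined then stands. State in Section 3.7 and the synopsis that the hematologic criterion covered CLL only. Removing the qualifier matters only if combination dosing is ever resumed.

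Cost: one table from data already collected, a sentence in two places, and some judgements on relatedness where the marrow is involved. The reported tolerability may become less favourable.

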3.10 CONCOMITANT THERAPY

3.10.1 Permitted Concomitant Therapy

Anti-emetics are permitted if clinically indicated. Standard supportive care medications are permitted as per institutional standards.

For subjects considered at risk for tumor lysis syndrome: Administer appropriate hydration and allopurinol or rasburicase per institutional standards before initiating treatment.

For subjects at risk for pneumonitis: In selected subjects (e.g., those with a history of recurrent pneumonias), anti-infectious prevention should be considered. Initiation of antibiotic prophylaxis against pneumocystis infection (e.g., with trimethoprim-sulfamethoxazole, dapsone, aerosolized pentamidine, or atovaquone) beginning before study drug administration may be warranted. Such supportive care may also offer the benefit of reducing the risk for other bacterial infections (Stern et al. 2014). Prophylaxis with intravenous Ig may be appropriate in subjects with low Ig levels (Raanani et al. 2009). Local practices or guidelines regarding infection prophylaxis may be followed.

For subjects at risk for infections: Bacterial/viral/fungal prophylaxis is allowed per institutional standards.

Protocol: ACE-LY-001

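### DLT criterion 2c names only Grade 3 febrile neutropenia, so read literally a Grade 4 or 5 event is a DLT only if it also meets another criterion

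*Protocol*

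**What the plan says.** Protocol Section 3.7 defines a Part 1 DLT as an ACP-319-related adverse event meeting one of three criteria, and the synopsis repeats the list.

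- Criterion 1: "Any Grade ≥3 nonhematologic toxicity", with an exception for Grade 3 nausea, vomiting or diarrhea that responds to supportive therapy.
- Criterion 2, introduced by "Any of the following hematologic toxicities (for CLL"): 2a is "Grade 4 neutropenia lasting >7 days", 2b concerns platelets, 2c is "Grade 3 febrile neutropenia (temperature ≥38.5°C"), and 2d concerns anemia.
- Criterion 3: a dosing delay of more than 28 consecutive days because of toxicity.

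Section 6.2.3 grades severity by CTCAE, from Grade 1 to Grade 5.

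Section 3.5 enrolls 6 subjects per cohort. At most 1 DLT in Cycle 1 allows escalation. Two or more suspend that dose and higher doses and set the MTD at the previous cohort. The MTD is the largest daily dose with DLTs in fewer than 33% of subjects. Section 5.1 says, without giving a probability, that these rules make escalation unlikely when the true DLT rate is high.

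**The concern.** A DLT definition should not count an event at one grade and leave out a worse grade of the same event. Criterion 2c does this as written: it fixes one grade, where criterion 1 in the same list runs upward from Grade 3. The synopsis has the same wording, so the two statements of the definition agree on the single grade.

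Criterion 1 does not clearly fill the gap. It is confined to nonhematologic toxicity, and the protocol places febrile neutropenia among the hematologic toxicities. A life-threatening or fatal case recorded under that term alone, with Grade 4 neutropenia of 7 days or less, would then not be a DLT.

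The DLT count is the only quantity in the written escalation rule and it defines the MTD. In a cohort of 6, one subject is enough to move the result across the boundary.

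**Working it through.** **1. The texts side by side.**

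| Place | Grade wording | Grades 4 and 5 covered? |
|---|---|---|
| Section 3.7, criterion 1 | Grade ≥3, nonhematologic | Yes |
| Section 3.7, criterion 2c | Grade 3 febrile neutropenia | No |
| Synopsis, criterion 2c | Grade 3 febrile neutropenia | No |
| Section 6.2.3 | Grades 1 to 5 | Scale runs to 5 |

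**2. The protocol's own rule.** 1/6 = 16.7%, below 33%; 2/6 = 33.3%, not below 33%. The split between at most 1 and at least 2 in 6 therefore agrees with the MTD definition. It also shows the leverage: a cohort with two true DLTs, one of them uncounted, is read as 1/6 (escalate) and not 2/6 (stop).

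**3. Effect on the chance of escalating.** The protocol states no probability, so there is no figure to reproduce. Let p be the true Cycle 1 DLT probability and m the share of true DLTs that the wording fails to count. The counted rate is q = p(1 − m). With 6 independent subjects,

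P(escalate) = (1 − q)^6 + 6q(1 − q)^5.

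Both p and m are assumptions. Worked cases:

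- p = 0.40, m = 0: q = 0.40; 0.0467 + 0.1866 = 0.233.
- p = 0.40, m = 0.25: q = 0.30; 0.1176 + 0.3025 = 0.420.
- p = 0.10, m = 0: q = 0.10; 0.5314 + 0.3543 = 0.886.
- p = 0.10, m = 0.25: q = 0.075; 0.6264 + 0.3047 = 0.931.

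Over a range:

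| True DLT rate p | All counted | 10% uncounted | 25% uncounted | 50% uncounted |
|---|---|---|---|---|
| 10% | 0.886 | 0.905 | 0.931 | 0.967 |
| 20% | 0.655 | 0.704 | 0.776 | 0.886 |
| 33.3% | 0.352 | 0.421 | 0.535 | 0.737 |
| 40% | 0.233 | 0.301 | 0.420 | 0.655 |
| 50% | 0.109 | 0.164 | 0.274 | 0.534 |

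The loss matters most where the true rate is high, which is where Section 5.1 claims protection. At low rates it is small.

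**4. What the documents say about frequency.** Section 1.13.2 reports febrile neutropenia as a serious event in 2 of 28 subjects (7%) on ACP-319 alone, without grades; the one DLT there was a hemolysis. This shows that the event occurs. It does not give the share of DLTs in the combination that would be Grade 4 or 5 febrile neutropenia missed by 2c.

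**The case against.** Several points on the other side stand.

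- **Other routes.** A severe case with a Grade ≥3 infection or other nonhematologic event counts under criterion 1, Grade 4 neutropenia of more than 7 days under 2a, and a long hold under criterion 3. Section 6.3.5 asks for reporting by diagnosis and for a death to be reported under its primary cause. The gap is therefore limited to events that meet none of those criteria.
- **Safety review.** Section 3.14 requires a teleconference before the next cohort enrolls, and related serious events and deaths are among the safety events discussed with investigators. Such an event would hardly go unseen. The written escalation rule still depends on the DLT count alone.
- **The CLL label.** Taken as literally as 2c, it confines all of criterion 2 to CLL. Section 3.5 puts CLL/SLL subjects on acalabrutinib alone under Amendment 3, while a DLT must be related to ACP-319. On that reading 2c reaches few or none under the current text, and other histologies have no explicit hematologic DLT. This does not rescue the grade wording; the label and the grade have to be settled together.
- **No dosing decision is left.** The Part 2 dose is fixed, ACP-319 was discontinued under Amendment 5, and all active subjects are on monotherapy under Amendment 6.

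A reader might also infer that growth factors let Grade 4 neutropenia be cut short of the 7-day limit in 2a. The documents do not support that. Table 3-2 does state that "neutrophil growth factors are permitted per ASCO guidelines", but as a parenthesis in a clause about neutropenia that has already lasted more than 7 days. Section 3.10.1 ("Standard supportive care medications are permitted as per institutional standards") names no growth factor. Shortening an episode below the limit is an inference. Nor is it a contradiction that criterion 2b counts "any requirement for platelets transfusion" while 2a has no matching clause: nothing in the protocol requires the platelet and neutrophil criteria to be parallel.

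**Conclusion.** The point holds in a narrow form. As written in Section 3.7 and the synopsis, 2c counts a Grade 3 febrile neutropenia and omits Grades 4 and 5 of the same event, unless criterion 1, 2a or 3 catches the case. The single grade may be a slip for an open range, but both places agree and nothing elsewhere corrects it. Because the count decides between 1/6 and 2/6, this is a fault in a decision threshold and not merely a missing detail.

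The size is not known. At an assumed true DLT rate of 40%, the chance of escalating goes from 23% to 30%, 42% or 66% as 10%, 25% or 50% of DLTs go uncounted. At an assumed 10% rate with 25% lost, it goes from 89% to 93%. These figures rest on independent subjects and assumed shares, and they are not evidence that any event was missed or that the Part 1 MTD is wrong. What remains open is whether the reported Part 1 DLT counts and MTD can be relied on, in a study whose primary objective is the safety profile.

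**What to change.** The sponsor should:

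1. Reconcile the grade wording of 2c with that of criterion 1, in both Section 3.7 and the synopsis, and clarify at the same time which histologies the CLL label on criterion 2 covers.
2. State how Grade 4 and Grade 5 febrile neutropenia was counted when the escalation decisions were made.
3. Tabulate the Part 1 Cycle 1 events (up to 18 subjects) by cohort, with and without those events as DLTs, and report whether any cohort's DLT count or the MTD changes.

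The choice of clinical rule stays with the sponsor, and no subject's treatment changes. The definition actually applied during escalation should stay visible next to any clarified wording, so that the report does not misstate the rule used at the time. The cost is a short clarification in two places and one small table. The downside is that a cohort's reported DLT count may rise.
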